9.2.2 Cohort Stopping Rules

9.2.2.1 Stopping Rules After Sentinel Dosing

The following events occurring in one sentinel subject will result in a temporary halt of dosing within that cohort:

- The occurrence of one SAE considered at least possibly related to the study drug.
- The occurrence of a CTCAE grade 3 considered at least possibly related to the study drug.

If any the above stopping rules is met, the remaining subjects of the cohort will not be dosed until the SRC reviews details of the event and/or additional data. If, after further review of the data, the SRC determines that no stopping rules have been met (e.g., AE determined to be unrelated to the study drug), then dosing of the remaining subjects of the cohort may proceed.

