8.2 Study Progression and Evaluations

A new cohort will not be dosed until the clinical portion of the preceding dose level has been completed, appropriate data has been reviewed by the SRC and authorization to proceed with the next dose level or next study part has been given by the SRC, as described in section 9.

Adjustment to the currently outlined dose levels and period of subjects' follow-up may be made by the SRC based on data from completed dose levels. However, the dose to be administered in a given cohort will not exceed the one currently outlined in the protocol.

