9.2 Dose Escalation and Stopping Rules

The following sections define stopping rules resulting in an immediate stop to dosing. Each section specifies whether the stop involves a final end of dosing or a temporary halt.

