9.2.1 Subject Stopping Rules

Dosing will be permanently stopped for any individual subject experiencing any of the following:

- SAE, regardless of causality to the study drug.
- An AE, physical examination abnormality, ECG abnormality, laboratory parameter abnormality, or vital sign abnormality, possibly or probably related to study drug, and either grade ≥ 3 (Common Terminology Criteria for Adverse Events [CTCAE], current version 5.0) or grade ≥ 2 and considered clinically significant by the SRC.
- Hypersensitivity or anaphylactic reaction related to study drug.
- Medical condition that is judged by the Investigator as to jeopardize the subject's safety if he/she continues to receive the study drug.
- QTc prolongation defined as QTcF increasing ≥ 60 msec and persisting for at least 10 minutes or QTcF > 500 msec and persisting for at least 30 minutes, or episode of torsade de pointes.
- Abnormal liver tests defined as:
 - \circ AST or ALT > 5X upper limit of normal (ULN).
 - \circ AST or ALT > 3X ULN along with one of the following criteria:

- Sustained for more than 2 weeks or
- total bilirubin level > 2X ULN or
- prothrombin time > 1.5X ULN or
- the appearance of fatigue, nausea, vomiting, right upper abdominal pain or tenderness, fever, rash, and/or eosinophilia (> 5%).
- \circ ALP > 3X ULN.
- o ALP > 2.5X ULN and total bilirubin > 2X ULN.
- o ALP > 2.5 ULN with the appearance of fatigue, nausea, vomiting, right upper abdominal pain or tenderness, fever, rash, and/or eosinophilia (> 5%).

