9.2.3.1 Events Within One Dose Level

Dose escalation will be halted if any of the events described below occur within one dose level:

- Individual stopping rules met for ≥ 2 subjects in the same cohort suggesting that subjects receiving higher dose levels would be at risk for similar adverse drug reactions.
- The occurrence of one SAE considered at least possibly related to the study drug.
- The occurrence of CTCAE grade 3 considered at least possibly related to the study drug in ≥ 2 subjects and independent of within or not within the same system organ class (SOC).
- Clinically significant abnormalities of the same character, at least of CTCAE grade 2, and considered at least possibly related to the study drug in ≥ 2 subjects, with regards to:

- o the physical examination;
- o ECG;
- o vital signs; or
- o clinical laboratory parameters.
- Mean exposure (AUC₀₋₂₄) exceeding 132 000 000 **ng.h/mL or concentrations** reaching 8 830 000 ng/mL.

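### The only explicit hold on undosed subjects in a cohort is tied to sentinel events; a first related grade 3 event in a non-sentinel triggers no such hold

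*Protocol*

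**What the plan says.** Section 9.2 of the protocol opens by saying: "The following sections define stopping rules resulting in an immediate stop to dosing". Each subsection is then meant to say whether its stop is final or temporary.

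- **9.2.1 (subject).** "Dosing will be permanently stopped for any individual subject experiencing any of the following". The list includes any SAE and any possibly or probably related event of grade 3 or higher.
- **9.2.2.1 (cohort, after sentinel dosing).** "The following events occurring in one sentinel subject will result in a temporary halt of dosing within that cohort". There are two triggers: one related SAE, and "The occurrence of a CTCAE grade 3 considered at least possibly related to the study drug". The consequence is that "the remaining subjects of the cohort will not be dosed until the SRC reviews details of the event and/or additional data". This is the only subsection under Cohort Stopping Rules.
- **9.2.3.1 (dose level).** "Dose escalation will be halted if any of the events described below occur within one dose level". One related SAE in any subject is enough. For grade 3 the condition is "The occurrence of CTCAE grade 3 considered at least possibly related to the study drug in ≥ 2 subjects".
- **9.2.4 (study).** The study ends after related SAEs in two or more subjects, the same related grade 3 event in two or more subjects, one related event of grade 4 or higher, or an SRC determination.

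Section 8.2 separately provides that "A new cohort will not be dosed until the clinical portion of the preceding dose level has been completed", and that the SRC must authorize the next level.

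Each cohort has two sentinels (one active, one placebo) and six non-sentinels (five active, one placebo; 11.3). Under 8.1 the non-sentinels are dosed no sooner than 48 hours after the sentinels and at least 15 minutes apart. Each infusion lasts about 60 minutes (11.6).

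**The concern.** In a single-dose study, stopping an individual subject has an effect only while his own infusion is running. After that, what matters at the same dose level is whether subjects not yet started are held. The plan writes that instruction for a sentinel event and not for a non-sentinel event, although most of the cohort is dosed in the second stage. After a first related, non-serious grade 3 event in a non-sentinel, a site following the stopping rules literally would find nothing that pauses the next infusion. After a first related SAE it would find a halt to escalation, which adds nothing express for the current level because 8.2 already keeps the next cohort closed until SRC authorization.

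The scheduled SRC meeting does not fill the gap. It takes place once Day 8 data exist for at least 7 of the 8 subjects (9.1), when the cohort is nearly or fully dosed. At stake is whether, in a first-in-human study, the pause is a written instruction or a matter of inference and discretion.

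**Working it through.** **Step 1: the rules side by side.** The event is taken to be the first of its kind in the study, so no cumulative rule is already part-met. Related means at least possibly related.

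| First event, one subject | In a sentinel | In a non-sentinel |
|---|---|---|
| Non-serious related grade 3 | 9.2.1 stops the subject; 9.2.2.1 holds the cohort | 9.2.1 stops the subject. The grade 3 rules in 9.2.3.1, 9.2.3.2 and 9.2.4 each need at least 2 subjects and are not met |
| Related SAE below grade 4 | 9.2.1; 9.2.2.1 holds the cohort; 9.2.3.1 halts escalation | 9.2.1; 9.2.3.1 halts escalation; no express hold at the same level |
| Related grade 4 or higher | 9.2.4 ends the study | 9.2.4 ends the study |

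The gap is therefore the non-sentinel cell in the first two rows. It is clear-cut in the first row and open to interpretation in the second.

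**Step 2: does the 9.2 lead-in close it?** For the SAE, a reader can combine the lead-in's immediate stop to dosing with the 9.2.3.1 trigger and infer a hold. But 9.2.3 words its own consequence as a halt of escalation, and on continued dosing it mentions only cohorts at lower dose levels. For the single grade 3 event, the only rule met is 9.2.1, so the lead-in supports a stop for that subject alone.

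**Step 3: how many subjects could a hold spare?** The plan states no figure to reproduce. Inputs: six non-sentinels (8.1, 11.3); minimum spacing 15 minutes (8.1), read as start to start because 11.6 sets the time of dosing at the start of infusion. Spacings of 30 and 60 minutes are assumptions. If the event occurs in the k-th non-sentinel, t minutes after his start, at constant spacing s:

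unstarted = max(0, 6 − k − floor(t/s)), averaged over k = 1 to 6.

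| s (min) | t = 30 | t = 60 | t = 90 |
|---|---|---|---|
| 15 | 3,2,1,0,0,0: 6/6 = 1.0 | 1,0,0,0,0,0: 1/6 = 0.17 | all 0: 0 |
| 30 (assumed) | 4,3,2,1,0,0: 10/6 = 1.67 | 3,2,1,0,0,0: 6/6 = 1.0 | 2,1,0,0,0,0: 3/6 = 0.5 |
| 60 (assumed) | 5,4,3,2,1,0: 15/6 = 2.5 | 4,3,2,1,0,0: 10/6 = 1.67 | 4,3,2,1,0,0: 10/6 = 1.67 |

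The most favourable case at 15 minutes is an event in the first non-sentinel. It leaves 5 unstarted before 15 minutes, 1 at 60 minutes, and 0 from 75 minutes (5 × 15).

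**Step 4: when would an event be seen?** The first scheduled post-dose vital signs and ECG are at 1.5 hours (11.9.1, 11.9.2), and the first post-dose laboratory tests are at about 48 hours (11.9.6). At 15-minute spacing all six have started by 75 minutes, before any of these. Earlier detection rests on clinical observation during infusion (11.10) and the injection-site checks at 0.5 and 1 hour (11.9.7).

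**The case against.** The strongest defence is that the tiering is deliberate. A sentinel event arises when one active subject has been exposed. By the time an active non-sentinel has an event, the active sentinel was dosed at least 48 hours earlier, so the count is at most 1 of 2, falling to 1 of 6. With a uniform prior (an assumption), the posterior mean event rate is (1+1)/(1+2) = 0.67 after 1 of 1, 2/4 = 0.50 after 1 of 2, and 2/8 = 0.25 after 1 of 6. A reader might argue that the same event carries the same information about risk whoever has it; on these counts it does not. This point stands. It does not remove the case for a written hold, because the consequence is only a temporary pause for review and a low threshold is reasonable for that.

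Discretion also covers much of the ground. The investigator or sponsor may withdraw a subject for safety (11.13), the investigator may terminate the study after consulting the sponsor (11.17), infusion reactions are evaluated by a physician on the spot (11.10), and nothing bars an ad hoc SRC meeting. Site procedures not included here may say more. All of this lowers the practical risk, but none of it makes the hold automatic in the protocol.

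Three stronger readings are tempting and unsupported:

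- **That the protocol lets dosing continue after a non-sentinel SAE.** It does not say so, and the 9.2 lead-in points the other way.
- **That five of the six active subjects per cohort are unprotected.** That is a headcount of who falls outside the trigger. An event in the last of them leaves no planned subject to hold.
- **That replacement subjects are exposed by the gap.** SRC consultation is already required before a replacement, and withdrawals for safety or tolerability are not replaced (11.13).

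**Conclusion.** The gap is real and narrow. The rules as written trigger no same-level hold after one non-serious related grade 3 event in a non-sentinel. After one related SAE below grade 4 they leave the hold to inference. Grade 4 or higher events and repeated events are already covered by 9.2.4.

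The benefit of closing it is modest. At the minimum spacing an average of 1.0, 0.17 and 0 subjects remain unstarted at 30, 60 and 90 minutes, so a hold matters mainly for clinically apparent events during infusion. It matters more if dosing is more widely spaced or spread over days; 8.1 sets no maximum spacing and no same-day requirement. These averages assume constant start-to-start spacing and an event equally likely in each of the six positions. The documents give no event rate, so no probability of needing the hold can be stated. The current amendment followed review of results up to Cohort 4, so a change could help only later cohorts, which carry the higher doses. This is a minor safety improvement.

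**What to change.** In 9.2.2.1, change the trigger from one sentinel to an event *occurring in any dosed subject of a cohort (sentinel or non-sentinel)*. State that all subjects not yet dosed at that dose level are held until an SRC review convened ad hoc. Retitle the section, since it would no longer concern sentinels alone. The two listed events and the wording on resuming dosing stay as they are, as do 9.2.1, 9.2.3 and 9.2.4.

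The cost is a few words in a protocol amendment. The operational downside is a possible short delay of part of a cohort for an event that may prove unrelated. Doses already diluted might also be lost, because 11.6 allows 4 hours at room temperature.

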9.2.3 Stopping Rules for Dose Escalation

Dose escalation will be temporary halted if the SRC suspects that any of the stopping rules described in sections 9.2.3.1 and 9.2.3.2 is met. Continuation or initiation of cohorts at lower dose levels will be evaluated on a case-by-case basis. If, after further review of the study data, it is determined by the SRC that no stopping rules have been met (e.g., AE determined to be unrelated to the study drug), then dose escalation may resume. However, if the SRC confirms that a stopping rule has been met, dose escalation will be stopped definitely for that part of the study.

9.2.3.1 Events Within One Dose Level

Dose escalation will be halted if any of the events described below occur within one dose level:

- Individual stopping rules met for ≥ 2 subjects in the same cohort suggesting that subjects receiving higher dose levels would be at risk for similar adverse drug reactions.
- The occurrence of one SAE considered at least possibly related to the study drug.
- The occurrence of CTCAE grade 3 considered at least possibly related to the study drug in ≥ 2 subjects and independent of within or not within the same system organ class (SOC).
- Clinically significant abnormalities of the same character, at least of CTCAE grade 2, and considered at least possibly related to the study drug in ≥ 2 subjects, with regards to:

- o the physical examination;
- o ECG;
- o vital signs; or
- o clinical laboratory parameters.
- Mean exposure (AUC₀₋₂₄) exceeding 132 000 000 **ng.h/mL or concentrations** reaching 8 830 000 ng/mL.

9.2.3.2 Cumulative Study Events

In addition to the events listed in section 9.2.3.1, any of the events described below occurring at different dose levels administered throughout the study (i.e., cumulative events) will also result in a temporary halt of dose escalation:

- The occurrence of CTCAE grade 3 of the same character considered at least possibly related to the study drug in ≥ 2 subjects.
- Clinically significant abnormalities of the same character, at least of CTCAE grade 2, and considered at least possibly related to the study drug in ≥ 3 subjects, with regards to:
 - o the physical examination;
 - o ECG:
 - o vital signs; or
 - o clinical laboratory parameters.
- Determination by the SRC that a pattern of AEs precludes further dose escalation, even if no other stopping rules have been met.

9.2.4 Study Stopping Rules

The study will be terminated if any of the following criteria are met:

- The occurrence SAEs considered at least possibly related to the study drug in ≥ 2 subjects and independent of within or not within the same SOC.
- If ≥ 2 subjects develop the same CTCAE grade 3 or if 1 subject develops a CTCAE grade 4 or higher, considered at least possibly related to the study drug.
- Determination by the SRC that a pattern of AEs precludes any further dosing.

10. Study Population

10.1 Sample Size

It is planned to enroll up to 80 male volunteers for participation in this study.

The study will consist of **8** cohorts, each including 8 subjects (6 subjects receiving the study drug NS101 and 2 receiving matching placebo), for a total of **64** subjects planned for evaluation.

Subjects who withdraw or are withdrawn from the study after dosing, for reasons other than safety and tolerability, may be replaced after consultation between the SRC members. The total number

of subjects dosed (including potential replacement subjects) will remain within a maximum of 10 subjects per cohort.

The sample size of this study is not determined based on statistical calculations, it is rather determined based on the probability of observing an AE. A sample size of 8 subjects per cohort randomized in a 3:1 ratio to the study drug versus placebo represents a typical panel for a FIH study. This number of subjects is judged adequate to achieve the study objectives. Therefore, up to 80 healthy adult male volunteers will be dosed.

10.2 Inclusion Criteria

Subjects enrolled in this study will be members of the community at large. The recruitment advertisements may use various media types (e.g., radio, newspaper, the clinical site Web site and volunteer database). Subjects must meet all of the following criteria to be included in the study:

- 1) Male, non-smokers (no use of tobacco or nicotine products within 6 months prior to screening), ≥18 and ≤55 years of age, with BMI >18.5 and <30.0 kg/m² and body weight ≥50.0 kg for males.
- 2) Healthy as defined by:
 - a) the absence of clinically significant illness and surgery within 4 weeks prior to dosing.
 - b) the absence of clinically significant history of neurological, endocrine, cardiovascular, respiratory, hematological, immunological, psychiatric, gastrointestinal, renal, hepatic, and metabolic disease.
- 3) Subject's score on the S-STS at screening must be 0.
- 4) Male subjects who are not vasectomized for at least 3 months prior to dosing, and who are sexually active with a female partner of childbearing potential (childbearing potential females are defined as women that are neither post-menopausal nor surgically sterile) must be willing to use one of the following acceptable contraceptive methods from the study treatment infusion and for 90 days after.
 - a) simultaneous use of condom and hormonal contraceptive used for at least 4 weeks or intrauterine contraceptive device placed for at least 4 weeks for the female partner;
 - b) simultaneous use of condom with spermicide and a diaphragm or cervical cap for the female partner.
- 5) Male subjects (including men who have had a vasectomy) with a pregnant partner must agree to use a condom from the study treatment infusion and for 90 days after.
- 6) Male subjects must be willing not to donate sperm for 90 days after study treatment infusion.
- 7) Capable of consent.

10.3 Exclusion Criteria

Subjects to whom any of the following applies will be excluded from the study:

- 1) Any clinically significant abnormality at physical examination, clinically significant abnormal laboratory test results or positive test for HIV, hepatitis B, or hepatitis C found during medical screening.
- 2) Positive urine drug screen or alcohol breath test at screening or admission.
- 3) History of asthma, urticaria, anaphylactic reactions, or any other clinically significant allergic reactions to any medication, including biologics, or food, or allergy to any excipient in the formulation.
- 4) Clinically significant ECG abnormalities (QTcF > 450 ms) or vital sign abnormalities (systolic BP lower than 90 or over 140 mmHg, diastolic BP lower than 50 or over 90 mmHg, HR less than 50 or over 100 bpm) at screening.
- 5) History of alcohol abuse within 1 year prior to screening or regular use of alcohol within 6 months prior to screening that exceeds 14 units of alcohol per week (1 unit = 150 mL of wine, 360 mL of beer, or 45 mL of 40% alcohol) or 3 to 4 units per day.
- 6) History of drug abuse within 1 year prior to screening or recreational use of soft drugs (such as marijuana) within 1 month or hard drugs (such as cocaine, PCP, crack, opioid derivatives including heroin, and amphetamine derivatives) within 3 months prior to screening.
- 7) Participation in a clinical research study involving the administration of an investigational or marketed drug or device within 30 days prior to study treatment infusion, administration of a biological product in the context of a clinical research study within 90 days prior to study treatment infusion, or concomitant participation in an investigational study involving no drug or device administration.
- 8) Use of medications for the timeframes specified below, with the exception of medications exempted by the Investigator on a case-by-case basis because they are judged unlikely to affect the PK profile of the study drug or subject safety (e.g., topical drug products without significant systemic absorption):
 - a) prescription medications within 14 days prior to study treatment infusion;
 - b) any vaccination, including COVID-19 vaccine, within 14 days prior to study treatment infusion:
 - c) over-the-counter products and natural health products (including herbal remedies such as St. John's wort, homeopathic and traditional medicines, probiotics, food supplements such as vitamins, minerals, amino acids, essential fatty acids, and protein supplements used in sports) within 7 days prior to study treatment infusion, with the exception of the occasional use of acetaminophen (up to 2 g daily);
 - d) depot injection or implant of any drug within 3 months prior to study treatment infusion.
- 9) Receiving treatment or participation in an organized weight loss program that may cause significant weight gain or loss within 1 month before dosing.
- 10) Donation of plasma or serum within 7 days prior to dosing. Donation or loss of blood (excluding volume drawn at screening) of 50 mL to 499 mL of blood within 30 days, or more than 499 mL within 56 days prior to study treatment infusion.

- 11) History of blood dyscrasias, including, but not limited to, thrombocytopenia, thrombocythaemia, or arterial/venous thromboembolic complications.
- 12) History of lymphatic disorders.
- 13) History of hypertriglyceridemia.
- 14) Current or history of malignancy.
- 15) Significant history of seizures, prior traumatic brain injury, schizophrenia, schizoaffective disorder, or bipolar disorder.
- 16) Any reason which, in the opinion of the Investigator, would prevent the subject from participating in the study.
- 17) For subjects in cohorts that will include a lumbar puncture (Cohorts 5 **to 8**): Medical conditions in which a lumbar puncture is contraindicated, including coagulopathy, thrombocytopenia, prior lumbar spinal surgery, or other factor that precludes safe lumbar puncture in the opinion of the Investigator.
- 18) For subjects in cohorts that will include a lumbar puncture (Cohorts 5 to 8): hypersensitivity to anesthetics, such as lidocaine, or any of its components.

11. Clinical Procedures

Unless otherwise specified, procedures, data collection and evaluation will be conducted as per the clinical site SOPs.

11.1 Screening Procedures

Subject screening procedures will be performed within 28 days preceding administration of study medication. Subjects must provide written informed consent prior to initiation of any screening procedures. The consent to perform some general screening procedures may be obtained on a consent document other than the Informed Consent Form (ICF) specific to this study, and therefore, some screening test results could be obtained before signature of the ICF specific to this study. The study-specific ICF must be signed and dated by the subject before participation to study-specific procedures.

Screening procedures will include: demographic data (age, gender, and handedness), medical and medication histories, complete physical examination, body measurements (height, weight, and BMI), ECG (12-lead), vital signs (BP, HR, RR, and OT), S-STS, hematology, biochemistry, coagulation, serology (HIV, hepatitis B and C tests), urinalysis, alcohol breath test, and urine drug screen.

For eligibility purposes, abnormal laboratory or vital signs results may be repeated once if abnormal result is observed at the initial reading. Moreover, abnormalities found in the ECG may need to be confirmed by repeated measurements. In the event that the participation of a subject in the study is delayed and some screening procedures had been performed outside of the prescribed screening window, outdated screening procedures can be repeated.

